The surveillance system will also be implemented in the study area at each health care level within the HDSS or equivalent surveillance system catchment area. Health care workers will record all outpatient visits (referral and non-referral) of subjects enrolled in the active surveillance up to the end of the active follow-up) on a register allowing for the collection of basic data (e.g. date of visit, clinical diagnoses and rapid testing confirmation, referral or treatment). In case appropriate registers are not available in the facilities, study registers should be developed. At enrolment, subjects participating in active surveillance will be given study specific stickers with the subject's study number. The stickers can be used on the health care facility's registers if no other system is in place to indicate a subject's visit and facilitate identification of data from enrolled subjects from the facility's register. The recorded data will be collected retrospectively on a regular basis and encoded in the eCRF.

CONFIDENTIAL

115055 (EPI-MALARIA-002 VS AME)
Protocol Amendment 7 Final

Every day, study staff will perform a round at hospitals and other health care facilities (with hospitalisation facility) to see all newly hospitalised children that could be eligible for the study. Parents/LARs of eligible children not yet enrolled into the study should be asked if they would agree to their child's participation and signed or witnessed and thumbprinted informed consent shall be obtained.

The monthly total number of hospitalised children < 5 years of age will be recorded in the logbook monthly for the study duration, for the purpose of the aggregated data analysis.

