	
2503 Subjects recruited in the group enhanced hospitalisation surveillance (EHS) :
 
 
Subjects eliminated if no hospitalisation recorded or without hospitalisation admission dates available
 
Subjects with ICF before hospitalisation date -1 day are eliminated
 
Subjects for whom the hospitalisation admission date is before ICF and: 
 
If hospital discharge date is known then subjects with ICF signed more than 7 days after hospital discharge are eliminated.
 
If hospital discharge date is missing with ICF signed more than 7 days after hospital admission are eliminated.
 
 
 

	
2504 Subjects recruited in the group active surveillance 6-12 weeks:
 
 
Subjects without DTP or without DTP vaccine dates available eliminated
 
Subjects eliminated if ICF signed more than 10 days after 1st DTP
 
Subjects eliminated if ICF signed after first visit available
 

\*This code should be allocated only in very special occasion for fraudulent subject (e.g. lab samples received by error).

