## 6. STATISTICAL METHODS

SAS version 9.4 or above will be used for statistical analysis.

All analyses will be conducted on the ATP cohort, unless otherwise detailed. The analyses will be done also on the Total cohort only if there are more than 5% of eliminated subjects; except for the demography where all the tables will be performed for both cohorts.

Main descriptive statistics (i.e. demographic characteristics) will be computed by study group, gender, EPI vaccine, study site and overall. Moreover, descriptive analysis of safety endpoints (i.e. AESI, Other AEs, meningitis) will be computed for specific sub-populations such as children with haemoglobinopathy and HIV-positive children.

Categorical variables will be summarised by the frequency and the percentage of each category. 95% confidence intervals (CIs) might also be presented and will be described in TFLs part. The following statistics will be presented for continuous variables: number of non-missing observations, mean, standard deviation, median, range (minimum and maximum) and 25th and 75th percentiles where required.

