## **6.9. Analysis of co-primary objectives**

### **6.9.1. Population**

The analysis of co-primary objectives will be done on the ATP cohort and will primarily include subject from AS. A secondary population will include the subjects from the active and enhanced hospitalisation surveillances for the computation of incidence for all children <5 years.

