#### 6.9.3.3. Incidence in children < 5 years

The IR of each and any AESI, of each and any other AE leading to hospitalisation or death (classified by the MedDRA SOC and PT level) and of aetiology confirmed meningitis will be estimated in all children < 5 years per 100,000 person per year. A 95% CI will be computed per year and overall using an exact method for a Poisson variable.

The numerator will be the number of cases of specified events (i.e. AESI) during the study period (in both AS and EHS grouped) and the denominator will be the person-years contribution of children in all communities < 5 years of age. The denominator will be computed using the census data. A census done at least once a year will provide the total number of children under 5 years.

For example, considering 5 census done between January 2015 and January 2017, a first subject recruited in March 2015 and a last subject recruited in April 2017:

The person-year (PY) will be computed as:

$$PY = N1 \cdot \text{Period1} + N2 \cdot \text{Period2} + N3 \cdot \text{Period3} + N4 \cdot \text{Period4} + N5 \cdot \text{Period5}$$

Contrary to the computation of IR following EPI vaccine or virtual vaccination where only the first event is counted in the numerator, for IR in children < 5 years, in case a subject had more than once the same AESI, all events will be counted in the numerator.

Confidence intervals [CI] will be computed using the exact method [[Clopper, 1934](#)].

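### The under-5 incidence counts events only in according-to-protocol subjects but divides by census person-years of all children under 5, so events lost to consent-timing or date codes bias it low

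*SAP*

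**What the plan says.** **Cohort.** SAP 6.9.1 states: "The analysis of co-primary objectives will be done on the ATP cohort and will primarily include subject from AS". The same section names AS plus EHS subjects as the secondary population for incidence in all children under 5. SAP 6 makes ATP the default for every analysis unless stated otherwise.

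**Rate.** SAP 6.9.3.3 counts events in AS and EHS together, repeats included. For the person-time, "the denominator will be the person-years contribution of children in all communities < 5 years of age", and "The denominator will be computed using the census data". Protocol 9.7.5.2.1 also specifies a whole-community denominator.

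**Eliminations.** Besides the eligibility code 2010, SAP 5.2 removes subjects under codes 2501 to 2504. The grounds are consent signed too late relative to the first DTP dose, the first visit or a hospital stay, and missing DTP dates or DTP vaccination. For EHS, code 2503 also removes subjects with no recorded admission or no admission date. Two further lines apply there: "If hospital discharge date is missing with ICF signed more than 7 days after hospital admission are eliminated" and "Subjects with ICF before hospitalisation date -1 day are eliminated".

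**Guard.** SAP 6 adds: "The analyses will be done also on the Total cohort only if there are more than 5% of eliminated subjects".

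**Logbook.** Protocol 9.4.2 says "The monthly total number of hospitalised children < 5 years of age will be recorded in the logbook monthly for the study duration", for an aggregated data analysis. The SAP makes no use of it in this rate.

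**The concern.** A population rate needs the events and the person-time to come from the same children. Here they do not. Apart from the ground of no recorded hospitalisation, the 2501 to 2504 grounds do not bear on whether an event was real or whether the child lived in the census area. Nor does late consent spoil the hospital data: Protocol 9.2.7.2.1 has routine data from before signature collected retrospectively once the form is signed. Yet elimination removes the child's events and leaves the child in the census count.

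The plan avoids this mismatch elsewhere. The post-dose rates in SAP 6.9.3.2 use AS ATP children for both events and person-time, and Protocol 9.7.7.2 leaves children whose parents refuse active surveillance out of the denominator.

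At stake is the under-5 background rate for AESI, other AE and aetiology-confirmed meningitis. SAP 6.10 carries the same method to the wider meningitis definitions, cerebral malaria, hospitalisation and death. Supplying background rates is the purpose of the study.

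**Working it through.** **1. The plan's own figure (Protocol 9.5, Table 7).** Inputs: a birth cohort of 11,500, five one-year age bands, two years.

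- Person-years = 11,500 × 5 × 2 = 115,000.
- 25 events: 25 / 115,000 = 21.7 per 100,000 person-years.
- Exact Poisson limits, chi-square(0.025; 50)/2 and chi-square(0.975; 52)/2 over 115,000, give 14.1 and 32.1.

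This agrees with Table 7. The table takes every event as counted.

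**2. Direction.** Let r be the share of enrolled cases that survive elimination. The census person-time does not change, so expected rate = true rate × r, with r at most 1. The effect is downward or nil.

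**3. Size.** No document gives r, so these values are assumptions. With 25 true cases over 115,000 person-years:

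| r (assumed) | Rate per 100,000 |
|---|---|
| 1.00 | 21.7 |
| 0.95 | 20.7 |
| 0.90 | 19.6 |
| 0.80 | 17.4 |

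The interval does not reveal the loss. At r = 0.80, 20 counted cases give 17.4 with limits 10.6 to 26.9, which looks like an ordinary result.

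**4. The 5% trigger.** SAP 6 does not say whether the 5% applies to all enrolled subjects or by group. Suppose it applies to all enrolled, with about 20,000 AS children (the SAP 2 target at implementing sites), no AS eliminations and E children in EHS. E is not given. Eliminations allowed without firing = 0.05 × (20,000 + E); as a share of EHS, e = 0.05 × (20,000 + E) / E.

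| E (assumed) | Eliminations allowed | Share of EHS, e |
|---|---|---|
| 2,000 | 1,100 | 55% |
| 5,000 | 1,250 | 25% |
| 10,000 | 1,500 | 15% |

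These are upper limits; any AS eliminations would use up part of the allowance.

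**5. From subjects to cases.** If a share f of the cases arise in EHS and these are eliminated at the same rate as EHS subjects generally, r = 1 − f × e. At e = 15%, r lies between 0.85 (all cases from EHS; 21.7 becomes 18.5) and 1 (none from EHS). Neither f nor e is in the documents.

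**The case against.** The best defence is that losses would be visible and the rate is secondary. SAP 6.9.3.1 tabulates endpoint counts on the Total enrolled cohort for AS and EHS and repeats those tables in the final report. SAP 6.2 shows enrolled and ATP numbers by site and group, and SAP 6.7 summarises deviations leading to exclusion. Above 5% a Total-cohort analysis is added. The main population is AS, where events and person-time match. SAP 6.9.3.3 does not itself repeat the word ATP, and it defers the computing method to a technical annex that is not among the documents. Protocol 9.2.1 expects high participation.

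Much of this limits the importance of the point. It does not remove it. The 6.9.3.1 tables are counts by site diagnosis, not rates of confirmed events. The trigger counts subjects and adds only a supplementary result. An unseen annex cannot be presumed to override the SAP body.

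Several stronger readings are tempting, and the documents do not support them:

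- *Every EHS elimination removes an event.* One ground in code 2503 is that no hospitalisation was recorded, and an EHS child need not have an AESI, meningitis or other AE.
- *Code 2503 removes every child re-admitted after consent.* Its consent-before-admission line could be read so, but Protocol 9.2.1.1 follows all later admissions, SAP 7.2.8 merges consecutive ones and 6.9.3.3 counts repeats. This is an ambiguity in wording.
- *Rates after vaccine introduction will look raised.* That needs capture or elimination to differ in EPI-MAL-003. Protocol 7.4 says events are monitored the same way, and a common capture fraction cancels in a ratio.
- *The bias varies by site with speed of consent.* No document gives data on this.
- *Refusals are part of the same fault.* Hospitalised children never enrolled also count only in the denominator, but that is a limit of consent-based surveillance, separate from the choice of ATP.

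**Conclusion.** The point stands as a should-fix. As written, the AS plus EHS numerator is ATP and the denominator is the whole census, so confirmed events in resident children eliminated only for consent timing or missing vaccination or visit dates are lost while their person-time remains. The direction is certain: downward, or nil if no case is eliminated. The size is unknown, since the documents give neither elimination rates nor the EHS enrolment; the figures above are scenarios.

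The conclusion rests on reading 6.9.1 and the section 6 default as governing 6.9.3.3, which is what the text says without an exception. It is confined to the under-5 rates; the post-dose AS rates are unaffected.

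**What to change.** - **Numerator.** In SAP 6.9.1 and 6.9.3.3, take it from the Total enrolled cohort: confirmed events in children who are under 5, resident in the census area and validly consented (no code 900), with a datable event inside the site's analysis window. State these conditions outright. Merely dropping ATP would readmit code 2010 violations such as a child aged 5 or over, and an event that cannot be dated cannot be placed after the site's Amendment 4 start.
- **ATP.** Keep it for the post-dose AS rates, and show the ATP-numerator under-5 rate as a sensitivity analysis.
- **Code 2503.** Say that its consent-date tests apply to the enrolling admission only.
- **Non-enrolment, separately.** Report by site and year the share of logbook under-5 admissions that were enrolled, as a descriptive check. A capture-corrected rate can only be a sensitivity analysis: it assumes that unenrolled admissions have the same event frequency as enrolled ones and that logbook totals are residents.

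The cost is SAP wording and a small amount of extra tabulation from data the protocol already collects. The downside is small: a few late-consent records enter the count.

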#### Management of first year of inclusion:

During the first year of inclusion (i.e. 2016), recruitment was done according to Protocol Amendment 3 where children had to be less than 3 years old with a corresponding census. As a consequence, IR in children < 5 years will be computed after the application on field of the Protocol Amendment 4:

- *Kintampo: 12 June 2017 in AS and 22 May 2017 in EHS*
- *Kombewa: 9 March 2017*
- *Navrongo: subjects entered directly under protocol amendment 4 (25 September 2017)*

The method to compute incidence will be described in a technical annex of the specific Mock TFL for the final analysis.

#### 6.9.4. Cumulative probability analysis

Kaplan-Meier curves presenting the cumulative probability of having at least one confirmed co-primary endpoint following EPI vaccine or virtual vaccination will be displayed.

This analysis will be performed on children enrolled in the AS ATP cohort.

The cumulative probability of presenting each event will be given with its 95% CI:

- After the primary schedule,
- After the secondary schedule.

In case an event occurs after several doses, only the first event will be taken into account.

## **6.10. Analysis of secondary safety objectives**

### **6.10.1. Population**

The same population as for the co-primary objectives (see Section [6.9.1](#)) will be used.

### **6.10.2. Meningitis cases**

#### **6.10.2.1. Meningitis cases monitoring**

As described in section [6.9.1](#), the number of cases of meningitis as well as the cumulative number of cases will be tabulated in the progress report for all meningitis diagnosis at the site level (based on first line laboratory results).

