9.2.4. Study period

Recruitment for active surveillance is expected to be done until the enrolment target is reached. Enrolment in enhanced hospitalisation surveillance has been early terminated for the sites where the RTS,S/AS01_E vaccine will not be implemented. For the sites where the RTS,S/AS01_E vaccine will be implemented, the enrolment in enhanced hospitalisation surveillance will end at start of study EPI-MAL-003.

Active surveillance will last 44 months for each subject (mimicking 24 months of active follow-up after the 4th dose of RTS,S/AS01_E in EPI-MAL-003) except for subjects enrolled from Burkina Faso sites for whom their participation in the study has been early terminated. The EPI-MAL-002 study will last for approximately 5 years (depending on recruitment timelines).

Note: There might be an overlap of studies EPI-MAL-002 and EPI-MAL-003, some children enrolled in EPI-MAL-002 may have the possibility to be part of EPI-MAL-003 (see Section [9.2.7.1.12](#) for more details).

The study began enrolment during Q4 2015.

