9.7.4.1. Sequence of analyses

Progress reports including listings and statistical tables for description of AESI, other AE leading to hospitalisation or death, meningitis and malaria, including severe malaria and cerebral malaria, will be produced every 6 months. Of note, data from Burkina Faso sites were part of the previous progress reports and will also be part of the progress reports planned up to Q4 2019.

An interim analysis will be performed when the RTS,S/AS01_E vaccine will be implemented in most of the study sites. This interim analysis will be done with clean data* collected on a sub-group of subjects from sites where the vaccine will be implemented having 6 months of follow-up following the administration of dose 3 of DTP/HepB/Hib vaccine (6-12 weeks group), or 6 months after V3 (5-17 months group); corresponding to V5.

Of note, further details will be provided in the SAP.

* Some data may change after the interim analysis as access to the eCRF will still be granted to sites and investigators throughout the follow-up period, until study conclusion.

Final analysis will be carried out on clean data collected on study conclusion.

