9.7.6.2. Statistical approach

- The incidence rate (and 95% CI) of probable meningitis, the incidence rate (and 95% CI) of aetiology-confirmed and/or probable meningitis and the incidence rate (and 95% CI) of aetiology-confirmed, probable and/or clinically suspected meningitis (final classification based on second line laboratory results and after external panel of experts review) will be estimated with the same approach as for aetiology-confirmed meningitis (described in Section 9.7.5.2.2).

(Amended 5 May 2020)

For all suspected meningitis at the site level (based on first line laboratory results), a monthly listing report will be checked by the monitoring and GSK safety teams and every 6 months the number of cases of meningitis as well as the cumulative number of cases will be tabulated in the Progress Report.

CONFIDENTIAL

115055 (EPI-MALARIA-002 VS AME)
Protocol Amendment 7 Final

- The incidence rate (and 95% CI) of cerebral malaria will be estimated with the same approach as for an AE as described in Section 9.7.5.2.
- Exposure determinants and potential risk factors for AESI and meningitis will be evaluated by means of univariate and multivariable Poisson regression models only for the incidence following DTP/HepB/Hib vaccine or virtual vaccination.

Adjusted covariates are described in Section 9.3.3:

- Study site.
- Demographic parameters such as age at reference date.
- Medical history and other risk factors such as chronic disease or diagnosed congenital disease, known HIV infection, malaria, malnutrition, drugs exposure, toxic agent exposure.
- Comorbidity factors such as premature birth, history of trauma.
- Health care seeking behaviour and distance to health care facilities.
- Type of health care facility.
- Neighbourhood of residence (urban/rural area).
- Total number of outpatient visits per centre.

The following strategy for covariate selection will be applied:

Covariates occurring in less than 5% of the subjects (percentage will be computed over subjects both in 6-12 weeks and 5-17 months group) will not be included in the model.

Of note, models will be run if a minimum number of cases of AESI or meningitis are observed (at least 10 cases in total).

Some predefined clinical relevant covariates might be forced into the models and will be listed in the SAP with the rationale (e.g. prior knowledge from literature).

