#### **3.2. Secondary Objectives**

In children living in the study area, prior to implementation of RTS,S/AS01E:

- To estimate the incidence of aetiology confirmed, and/or probable meningitis (final classification).
- To estimate the incidence of probable meningitis (final classification).
- To estimate the incidence of aetiology confirmed, probable and/or clinically suspected meningitis (final classification).
- To monitor trends over time of meningitis cases identified at site level (first line laboratory).
- To describe risk factors for AESI, other AE leading to hospitalisation or death, meningitis and malaria.
- To describe the causes of hospitalisation (including AESI, other AE, meningitis and malaria).
- To describe the causes of death, overall and by gender.
- To assess the risk of febrile convulsions during the 7-day period and 1-month period following administration of routine EPI vaccines.

---

 Acute disseminated encephalomyelitis (ADEM), encephalitis, Guillain-Barre Syndrome, hypotonic hypo responsive episode (HHE), general convulsive seizure  
Intussusception, hepatic failure or renal insufficiency  
Juvenile chronic arthritis, Stevens-Johnson syndrome/toxic epidermal necrolysis, Henoch-Schonlein purpura, Kawasaki disease  
Diabetes mellitus type I, thrombocytopenia, anaphylaxis

- To estimate the incidence of any malaria (including *P. falciparum* malaria) diagnosed by rapid diagnostic test (RDT) and/or microscopy.
- To estimate the incidence of severe malaria (including *P. falciparum* malaria) diagnosed by RDT and/or microscopy.
- To estimate the incidence of cerebral malaria (malaria diagnosed by RDT and/or microscopy).
- To estimate the prevalence of anaemia among hospitalised children.
- To estimate the incidence of all-cause hospitalisations and hospitalisations attributed to malaria (including *P. falciparum*).
- To estimate the mortality rate (all-cause mortality and deaths attributed to malaria [including *P. falciparum*]), overall and by gender.

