## 6.9.3. Incidence of co-primary endpoints

### 6.9.3.1. Description of the events

The occurrence of the following endpoints will be regularly (every 6 months) reported in progress reports [[Progress Report](#)] on the total enrolled cohort for hospitalised cases and outpatient visits when applicable:

- Each AESI according to site diagnosis,
- Other AE leading to hospitalisation or death, according to site diagnosis
- First line laboratory meningitis diagnosis according to site diagnosis following protocol definition (i.e. Bacterial confirmed meningitis, probable meningitis, clinically suspected meningitis).
- Malaria cases reported during outpatient visit or at hospital:
  - Clinically diagnosed Malaria
  - Any uncomplicated malaria (including *P. falciparum* malaria)
  - Any severe malaria (including *P. falciparum* malaria)
  - Severe *P. falciparum* malaria
  - Severe *P. vivax*
  - Cerebral malaria

- Fatal malaria cases
- Death reported at hospital or at home classified by MedDRA PT from study conclusion.

The number of subjects (%) reporting at least once each endpoint as well as the total number of events listed above and the number of associated outpatient visits/hospitalisations will be presented for both AS and EHS by EPI vaccination status and by gender. MedDRA SOC and PT level will be displayed for those safety endpoints.

Progress reports will include individual listings and statistical tables. The same tables and listings will also be presented for the final report.

Descriptive data in the progress report will also be presented:

- The demographic census will be presented by study site and by age group according to gender and overall.
- The number of subjects enrolled will be presented by study site, by study group and according to EPI vaccination status.
- The evolution of enrolment will be presented separately for each study group.
- Population characteristics (age at informed consent, gender) will be described by study group according to EPI vaccine received.
- The number and percentage of subjects who received the EPI vaccine doses will be summarised for EPI vaccinated subjects by each study group according to gender and overall.

And descriptive analysis of quality indicators (see section 6.10.7) will be done:

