- The percentage of subjects reporting abscess at injection site within 7 days (day of vaccination and 6 subsequent days) after each dose of the DTP/HepB/Hib vaccine will be reported for each dose and overall according to gender and overall.
- As negative control, the prevalence of foot positional deformations will be presented according to gender and overall.

Of note, each progress report will be done on uncleaned data and will present cumulative results. The same analysis will be performed for the interim analysis on cumulative cleaned data. ***The final analysis will be done only on confirmed cases according to the protocol case definitions.***

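### The objective to follow first-line meningitis over time is given case counts but no person-time rate, while the population under surveillance changes in documented steps

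*SAP*

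**What the plan says.** Following first-line meningitis over time is a secondary objective (protocol 8.2, SAP 3.2). Protocol 9.2.5.3 sets up a first-line laboratory classification for this purpose. It reserves a separate final classification, made after second-line testing and expert review, for the statistical analyses.

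The analysis named for the objective is a count. SAP 6.10.2.1 says that "the number of cases of meningitis as well as the cumulative number of cases will be tabulated in the progress report". Protocol 9.7.6.2 says that "every 6 months the number of cases of meningitis as well as the cumulative number of cases will be tabulated in the Progress Report", and adds a monthly check of a case listing. SAP 6.9.3.1 describes the progress-report tables, which include first-line meningitis: "The number of subjects (%) reporting at least once each endpoint as well as the total number of events listed above" are shown by surveillance type, EPI vaccination status and gender. It also states that "each progress report will be done on uncleaned data and will present cumulative results". The same report shows the census by site and age group, and enrolment by site and over time.

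The dates at which coverage changes are also documented:

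- **Age range.** First-year recruitment ran under Amendment 3, "where children had to be less than 3 years old with a corresponding census" (SAP 6.9.3.3). Amendment 4, with its limit of 5 years, was applied at Kombewa on 9 March 2017 and at Kintampo on 22 May 2017 (EHS) and 12 June 2017 (active surveillance).
- **Site entry.** Navrongo joined on 25 September 2017 (SAP 6.9.3.3).
- **Site exit.** The two Burkina Faso sites stopped surveillance on 6 June 2018 (protocol 9.2). Their data nevertheless stay in these reports until Q4 2019; protocol 9.7.4.1 notes that "data from Burkina Faso sites were part of the previous progress reports and will also be part of the progress reports planned".
- **EHS closure.** In the implementing sites "the enrolment in enhanced hospitalisation surveillance will end at start of study EPI-MAL-003" (protocol 9.2.4), and that study started in Q1 2019 (protocol 7.4).

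**The concern.** A half-yearly case count is the product of incidence, population covered and time. When the population covered moves in steps, the count moves with it even if incidence is flat, and a real change in incidence can be offset by a step in the other direction. The cumulative count is less informative still, since it can only rise.

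Meningitis is a potential risk of the vaccine (protocol 7.2). The phase III cases came mainly from two sites, one of which, Kombewa, is analysed here. Protocol 9.9 expects outbreaks in some sites and asks for rates to be read against each site's epidemiology. The first-line series is the one assigned to follow time trends, so it should be readable as incidence.

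**Working it through.** **Inputs.** Birth cohort per year: 17,250 in all sites and 11,500 in implementing sites (protocol 9.2.1). Active surveillance: about 20,000 children in implementing sites (protocol 9.7). Illustrative rate: 25 events in 115,000 person-years (protocol Table 7). This rate is a precision example, not a meningitis estimate.

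**Reproducing the plan's figure.** Person-years = cohort × 5 age bands × 2 years = 11,500 × 5 × 2 = 115,000. Rate = 25/115,000 = 21.7 per 100,000. The exact Poisson limits are χ²(0.025; 2k)/2 and χ²(0.975; 2k+2)/2, each divided by person-years. For k = 25 they give 14.1 and 32.1, as in Table 7. The other three rows of that table also reproduce.

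**Expected cases per six months at a constant 21.7 per 100,000.** Expected count = rate × population × 0.5, with equal one-year age bands and the same incidence at every age (assumptions).

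| Population under surveillance | Children | Person-years in 6 months | Expected cases |
|---|---|---|---|
| Under 3, cohort 11,500 | 11,500 × 3 = 34,500 | 17,250 | 3.75 |
| Under 5, cohort 11,500 | 11,500 × 5 = 57,500 | 28,750 | 6.25 |
| Under 5, cohort 17,250 | 17,250 × 5 = 86,250 | 43,125 | 9.4 |
| Active surveillance only | 20,000 | 10,000 | 2.2 |

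**Step sizes.**

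- Age widening: 5/3 = 1.67, a rise of 67%.
- Loss of the non-implementing sites: 11,500/17,250 = 0.67, a fall of one third.
- EHS closure: 20,000/57,500 = 0.35.

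These ratios do not depend on the rate. At 4.3 per 100,000 the age step is 0.75 to 1.25 cases, and at 43.5 it is 7.5 to 12.5. Divided by its person-years, every row returns 21.7.

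**Masking.** A true fall in incidence of 1 − 3/5 = 40%, coinciding with the age widening, would leave the count unchanged.

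**Sensitivity to age.** Let φ be the incidence at 3 to 4 years relative to under 3. The age step then raises the count by (2/3)φ: 67% at φ = 1, and 33% at φ = 0.5 (assumed values). If φ is not 1, a crude rate also shifts when the age range widens, which is why a series with a fixed age range is needed.

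**Cell sizes.** At the illustrative rate, 6.25 cases per half-year over three sites is about 2 per site. The exact 95% interval for 2 events is 0.24 to 7.2, a roughly 30-fold range. A site-year would hold about 12.5/3 ≈ 4 cases.

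**The case against.** The strongest reply is that the plan already has most of what is asked for, and that several stronger readings fail.

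- A reader might infer that meningitis has no calendar-time analysis. It has one. SAP 6.9.3.3 gives yearly incidence on census person-years with exact Poisson intervals for aetiology-confirmed meningitis, and 6.10.2.2 extends the under-5 approach to the other groupings. These rates start at each site's Amendment 4 date and exclude Burkina Faso (SAP 6.1), so two of the steps are already handled there.
- A reader might infer that no denominators exist, or that uncleaned counts are the only monitoring. The progress report carries percentages, census and enrolment (SAP 6.9.3.1). Protocol 9.7.6.2 adds the monthly listing check. The interim analysis repeats the tables on cleaned data.
- A reader might infer that an outbreak in one site would be hidden. SAP 6.2 tabulates meningitis by study site, and nothing in 6.10.2.1 says that the count is pooled.
- Protocol 9.2.5.3 deliberately separates first-line monitoring from the final classification used for inference. The progress-report template and mock tables are separate documents, not available here, and may show period and site.

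All of this narrows the point without removing it. The yearly rates are not first-line, and no census-based rate covers the Amendment 3 period. A cumulative percentage of enrolled subjects is not an incidence, least of all for EHS children, who enter because they are in hospital. The census and the cases sit in the same report but are not combined. The place of the first-line series in the final report is also unclear. SAP 6.9.3.1 says that the progress tables will be repeated there, but also limits the final analysis to confirmed cases, and Table 5 lists meningitis by final diagnosis only.

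**Conclusion.** The point holds in a limited form. The first-line trend objective is analysed by counts and cumulative counts, with no person-time rate specified, across a period in which coverage changes by design. Changes in those counts therefore cannot be attributed to incidence.

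The 67% for the age widening rests on equal age bands and equal incidence by age. It applies site by site, at the dates given for Kombewa and Kintampo; the SAP gives no Amendment 4 date for Burkina Faso. The one-third loss and the factor of 0.35 at EHS closure use planning figures and treat all sites as active together, so they are illustrative.

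The objective is secondary and descriptive, and no co-primary estimate changes. The amendment is worth making because the data are already held.

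**What to change.** In SAP 6.10.2.1, add one final-report table on cleaned data for the three analysed sites. It should give non-cumulative first-line cases per period, divided by census person-years for the age range then under surveillance, with exact Poisson 95% intervals.

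- Show half-yearly rates overall and yearly rates by site, because half-yearly site cells would hold very few cases.
- Give a fixed under-3 series where the census data allow it, and an under-5 series from each site's Amendment 4 date. State which of Kintampo's two dates is used.
- End both series at EHS closure, because ascertainment after that covers active-surveillance children only and no longer matches a census denominator.
- Mark the coverage-change dates on the table.

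At the same time, correct the cross-reference in 6.10.2.1: it points to 6.9.1 (population), whereas the progress-report description is in 6.9.3.1.

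The cost is one extra table from case and census data already collected, with wide intervals in the smaller cells.
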